30 fusional amplitudes, may be responsible for recurrence of the exotropia following treatment.

31 To provide context for the proposed randomized clinical trial (RCT), the following summary
32 briefly describes commonly used management strategies along with data from previous RCTs.

33 **1.2.1 Observation**

34 We are aware of two previous RCTs in which subjects with IXT were randomized to
35 observation. The PEDIG IXT2 studies^{22,23} randomized children to observation versus part-time
36 patching. In the older cohort randomized to observation (3 to < 10 years at enrollment),
37 deterioration of IXT (constant exotropia $\geq 10\Delta$ at distance and near or ≥ 2 -octave decrease in near
38 stereoacuity from the best previous measure, or being prescribed treatment despite not having
39 met motor or stereo deterioration) was met in 25 of 183 by 3 years (15%, 95% confidence
40 interval = 10%-22%), 12 of whom were prescribed treatment without meeting motor or
41 stereoacuity criteria.²⁴ However, of the 132 who completed the 3-year visit and had not been

42 treated during the study, only 1 (<1%) met motor or stereoacuity deterioration criteria at 3
 43 years.²⁴ Of those older children randomized to observation who remained untreated over the 3
 44 years, “complete or near complete resolution” (exodeviation <10Δ at distance and near, no
 45 reduction in stereoacuity, and no other nonsurgical treatment for IXT, having never met
 46 deterioration criteria) was met in 6 (7%) of 86.²⁵

47 In the younger cohort randomized to observation (12-35 months at enrollment), deterioration of
 48 IXT (constant exotropia ≥10 prism diopters at distance and near or treatment prescribed despite
 49 not having met motor deterioration) occurred in 28% (95% CI = 20%–39%) by 3 years.²⁶ Of the
 50 24 participants meeting the primary outcome of deterioration, seven met motor deterioration and
 51 17 were prescribed treatment without meeting motor deterioration.²⁶ The cumulative probability
 52 of motor deterioration by 3 years was 10% (95% CI = 5%–19%).

53 In a pilot RCT of surgery versus observation for IXT, Clarke et al²⁷ found 2 (9%) of 22 in the
 54 observation group showed significant improvement in control (improved 3 and 4 points on the
 55 office control scale) after 9 months of follow-up.

56 **1.2.2 Surgery**

57 The aim of surgery for IXT is to reduce the magnitude of the exodeviation (or eliminate it

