 142 points). Angle of deviation improved 0.2 Δ in the observation group and 2.3 Δ in the patching
 143 group (mean difference 2.1 Δ (0.6 to 3.6 Δ)).

144 Nevertheless, in both the 12- to 35-month and 3- to <11-year-old cohorts, many participants had
 145 persistent intermittent exotropia post-treatment. Changes in suppression or fusional amplitudes,
 146 and relationships with better versus worse control, were not evaluated.

147 **1.3.3 Previous Non-randomized Studies of Patching Treatment**

148 A small number of non-randomized studies have evaluated patching for IXT.^{16,36,37} While there
 149 are intrinsic challenges when interpreting data from non-randomized studies, the following are
 150 selected for more detailed review either because they provide additional information on potential
 151 effects of full-time patching, and/or provide some insight regarding how patching may impact
 152 sensory adaptations, the angle of deviation, or fusional amplitudes.

153 **Full-time Patching**

154 Jacobucci & Henderson 1965³³: Twenty-eight children with IXT, scheduled for surgery, were
 155 selected (“at random”) for full-time patching for 3 months. IXT control and angle of deviation
 156 were compared with a control group of 38 children undergoing anti-suppression and diplopia
 157 therapy. Distance angle of deviation by PACT reduced by a mean of 5.8 \pm 1.1 Δ from baseline to 3
 158 months in the patching group, compared with an increase of 1.8 \pm 0.4 Δ in the control group. Near
 159 angle of deviation by PACT reduced by a mean of 4.6 \pm 1 Δ from baseline to 3 months in the
 160 patching group, compared with an increase of 1.3 \pm 0.5 Δ in the control group. Eleven of 28
 161 patched patients and 20 of 38 control patients were constant exotropia at distance at baseline; of
 162 these, 8 (73%) of 11 in the patching group and 0 of 20 in the control group became intermittent
 163 or phoric at 3 months.

164 Flynn et al 1976³²: In a prospective study, Flynn and colleagues prescribed full-time patching for
 165 4-12 weeks to 31 children (mean age 7.6 years, range 3 to 13 years) with IXT. Mean angle of
 166 deviation pre-treatment was 20 \pm 7 Δ at distance and 15 \pm 12 Δ at near. Nine of 31 had undergone
 167 previous surgery. Following patching treatment, 7 (23%) of 31 showed dramatic improvement
 168 such that “the deviation became almost completely phoric, fusion improved, and all evidence of

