 169 suppression on the synoptophore or in free space disappeared.” Fourteen of 31 patients had a
 170 reduction in angle of deviation and a change from tropia to intermittent tropia or phoria. In 12 of

171 31 patients there was a measurable improvement in suppression with disappearance of the
 172 suppression scotoma. Increase in the range of fusional amplitudes occurred in 9 of these 12
 173 patients. Of note, Flynn et al³² report that some patients did not respond positively to patching,
 174 with 12 showing an increase in angle of deviation (mean 5Δ , range 2Δ to 15Δ) and 6 showing
 175 worsening control. Long-term follow-up was not reported.

176 **1.4 Mechanism of Patching Treatment Effect**

177 Patching is considered “anti-suppression” therapy, affecting exodeviation control by reducing or
 178 eliminating the suppression that occurs when the exodeviation is manifest.^{32,33,38,39}

179 **1.4.1 Suppression**

180 Previous studies have attempted to evaluate the presence versus absence of suppression, as well
 181 as the size and location of the suppression scotoma when the exodeviation is manifest,^{15,18,40-44}
 182 but few have evaluated changes in suppression with treatment or the relationship between
 183 suppression status and treatment success. In fact, although patching is designated “anti-
 184 suppression” treatment, there are few data demonstrating that changes in suppression occur with
 185 patching.

186 It has been suggested that, left untreated, suppression in many children with IXT will increase,⁴¹
 187 making it harder to remediate and leading to poorer treatment outcomes, but this has not been
 188 studied. It has also been suggested that eradication of suppression is required for successful
 189 treatment,¹⁵ but this deserves further study.

190 **1.4.2 Fusional Vergence Amplitudes**

191 Motor fusion mechanisms are responsible for maintaining binocular alignment, and in IXT, both
 192 convergence and divergence are thought to be important for enabling motor control of the
 193 exodeviation.^{45,46} In previous studies,^{32,38,47,48} data suggest that patching results in an increase in
 194 convergence amplitudes, but further study is needed to verify whether such changes truly occur
 195 and if they do, whether they are directly related to changes in suppression or occur
 196 independently. It is also unknown how such changes relate to improvement or successful
 197 treatment of IXT.

198 **1.4.3 Magnitude of Deviation**

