231 IXT is a common eye condition, but long-term surgical treatment outcomes are disappointing,
 232 with high failure rates due to recurrence or undercorrection of the exodeviation. Patching is a
 233 commonly used nonsurgical treatment for which there is some evidence of short-term treatment
 234 benefit (improved exodeviation control and reduced angle of deviation) when prescribed 2-3
 235 hours/day. Nevertheless, the extent to which patching is effective if worn for long periods of
 236 time per day or if any treatment effect is sustained once treatment is discontinued is unknown.

237 Understanding the effectiveness of patching treatment and whether there is a benefit from full-
 238 time patching versus observation alone has important implications for managing children with
 239 IXT. If full-time patching is associated with more improvement in distance control compared to
 240 observation alone, then future studies can be conducted to evaluate different durations of full-
 241 time patching treatment, whether the effect is maintained off-treatment, and how full-time
 242 patching compares to other treatment strategies.

243 In addition, this study would provide evidence of the ability of patching to alter suppression,
 244 anomalous retinal correspondence, and fusional amplitudes, and the relationships of these
 245 clinical characteristics with treatment success, failure, and improvement of IXT. This study
 246 provides an opportunity to explore such relationships, and data are expected to create hypotheses
 247 for future studies.

248 **1.8 Study Objectives**

249 Determine whether full-time patching is more effective than observation for improving distance
 250 control of IXT after 3 months of treatment (on-treatment outcome).

251

252 **1.9 Potential Risks and Benefits of Study Treatment**

253 **1.9.1 Known Potential Risks**

254 There is a risk that patching may create diplopia that then becomes troublesome to the patient,
 255 but this complication is seldom reported. It is possible that some patients will show worsening of
 256 IXT control or increase in magnitude with patching³² or observation,²² but deterioration criteria
 257 will be assessed after 3 months and the short 3-month duration allows for cessation of patching
 258 treatment and/or commencement of other treatment should deterioration of the IXT occur. Skin
 259 irritation may occur. If persistent skin irritation occurs due to the adhesive patch, the participant

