3.2 Angle of Deviation

- 134 At 3 months, the angle of deviation by PACT will be described using mean, SD, and range, and compared
- between treatment groups using an ANCOVA model, adjusting for baseline PACT angle. The analysis will
- be completed separately for the distance and near angles. Esodeviations will be represented using a
- negative sign to differentiate them from exodeviation.

138 139

- Additionally, the proportions of participants with improvement of distance angle and improvement of near
- angle (separately) at 3 months greater than the test/retest variability will be compared between the
- treatment groups using Barnard's test. The treatment group difference and 95% confidence interval will be
- estimated by inverting Barnard's test, using the method of Agresti and Min.² The published test-retest
- 143 criteria³ are as follows:

144 145

146

147

149

At distance:

- If deviation magnitude $\leq 20 \Delta$, $\geq 4 \Delta$ decrease exceeds test-retest variability
- If deviation magnitude $\geq 20 \Delta, \geq 8 \Delta$ decrease exceeds test-retest variability

148 At near:

- If deviation magnitude $\leq 20 \Delta$, $\geq 7 \Delta$ decrease exceeds test-retest variability
- If deviation magnitude >20 Δ , \geq 13 Δ decrease exceeds test-retest variability

150 151

- Development of an esodeviation ≥ 4 Δ will not be counted as an "improvement in angle" in these analyses.
- Also, although the same guidelines above apply to classifying increases in angle as beyond test-retest
- variability, only decreases in angle are of interest here.

155156

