8.1 Deterioration

The number and proportion of participants with deterioration, as defined below, will be tabulated for each treatment group at 3 months as a safety outcome. Treatment group differences will not be reported.

324 325

327

328

329

330

- Deterioration is defined as meeting one of the following criteria at the 3-month follow-up visit:
- 326 1) Constant exotropia at least 10Δ at distance AND near by SPCT:
 - a) Constant is defined as an exotropia present throughout the examination and confirmed by cover/uncover testing performed at least 3 different times over the course of the exam (including during assessment of IXT control).
 - 2) Decrease in near stereoacuity of at least 2 levels from baseline, or to nil, measured using the Randot Preschool Stereotest.

331332333

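### Worsening of control or angle is a named risk, but no planned table counts the children who worsen

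*SAP*

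**What the plan says.** **The risk.** Protocol 1.9.1 says "It is possible that some patients will show worsening of" control, or a larger deviation, under patching or observation. It answers this by pointing to the deterioration criteria, which "will be assessed after 3 months and the short 3-month duration allows for cessation of patching" or a move to other treatment if deterioration occurs.

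**The safety outcomes.** SAP 8.1 reads "Deterioration is defined as meeting one of the following criteria at the 3-month follow-up visit". There are two criteria: constant exotropia of at least 10 PD by SPCT at distance and also at near; or a near stereoacuity loss of at least 2 levels, or to nil. SAP 8.2 tabulates visual acuity loss and SAP 8.3 tabulates diplopia. All of SAP 8 uses only visits inside the analysis window.

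**The efficacy analyses.** The primary outcome (SAP 2) is a signed change, positive when worse, tested two-sided. SAP 3.1 adds the proportion improving by 2 or more points in control, at distance and near. SAP 3.2 describes the 3-month angle by mean, SD and range, compares it by ANCOVA, and adds the proportion whose angle falls by more than test-retest variability. It says the same limits would classify increases, then that "only decreases in angle are of interest here".

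**Background.** In the full-time patching series described in Protocol 1.3.3, given for "4-12 weeks to 31 children (mean age 7.6 years, range 3 to 13 years) with IXT", some children did not respond, with "12 showing an increase in angle of deviation (mean 5Δ , range 2Δ to 15Δ) and 6 showing" worse control.

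**The concern.** The protocol recognises that children may go in either direction. The proportion analyses look in one direction, and the safety outcome set against this risk has a much higher bar than the risk itself. If most patched children improve and some worsen, the mean difference and the responder proportion can both favour patching while the report never says how many children got worse. The trial would then be silent on a risk that it names, although the measurements and, for angle, the cut-offs are already in hand.

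**Working it through.** **1. Would the deterioration criteria catch the named risk?** Two cases, each with near still intermittent and stereoacuity unchanged:
- The distance angle rises from 25 to 40 PD. The rise of 15 PD exceeds the 8 PD distance limit in SAP 3.2. It is not deterioration, because near is not constant. Both values lie inside the 15 to 50 PD entry range, so the range of 3-month angles need not reveal it either.
- Mean distance control goes from 2.0 to 5.0 at distance only. This is the largest worsening that SAP 2 allows (+3.0), and again it is not deterioration.

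Neither child appears in a SAP 8 table unless acuity or diplopia also changes.

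**2. Would the mean analyses show it?** A net worsening would show. A minority need not. As an illustration only, let 12/31 = 38.7% of a group worsen by 5 PD and the rest improve by x. For a net improvement of 2.3 PD (the part-time patching mean in Protocol 1.3.2):

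0.387 × 5 − 0.613 × x = −2.3, so x = (2.3 + 1.94) / 0.613 = 6.9 PD.

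The mean looks like a benefit while more than a third have a larger angle.

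**3. The plan's own sample size, to confirm the inputs.** Protocol 7.3 gives difference 1.15, SD of change 1.5, correlation 0.30, two-sided 5%, 90% power.
- Residual SD = 1.5 × √(1 − 0.30²) = 1.431.
- Noncentral t with 2n − 3 degrees of freedom gives 34 per arm, 68 in total, as stated (the plain normal formula gives 33 per arm).
- 68 / 0.95 = 71.6, rounded up to 72, as stated.

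**4. How much worsening those inputs imply.** Take improvement in control as normal with mean m and SD s. Then P(any worsening) = Φ(−m/s) and P(worse by 2 or more points) = Φ((−m − 2)/s). The means and the SD of 1.5 are the planning values; 1.23 is the observation-group SD in Protocol Table 1.

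| Arm | m | s | Any worsening | Worse by ≥2 points |
|---|---|---|---|---|
| Patching | 1.45 | 1.5 | Φ(−0.967) = 16.7% | Φ(−2.30) = 1.1% |
| Observation | 0.30 | 1.5 | Φ(−0.20) = 42.1% | Φ(−1.53) = 6.3% |
| Observation | 0.30 | 1.23 | Φ(−0.244) = 40.4% | Φ(−1.87) = 3.1% |

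In 36 patched children, 16.7% is about 6 with a worse score even if the trial succeeds as planned. At the 2-point threshold, the expected counts per 36 are about 0.4 patched and 1.1 to 2.3 observed.

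**5. The cited series, as background.** Worse control 6/31 = 19% (exact 95% CI 7% to 37%); larger angle 12/31 = 39% (22% to 58%), counting any rise from 2 PD up.

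**6. What a by-arm count could show.** A count of 7 of 36 (19%) has an exact 95% CI of 8% to 36%. With 34 per arm, 19% against an assumed 5% or 10% has 43% or 18% power. The table can describe but not test.

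**The case against.** **Increases are analysed.** A reader might infer that the SAP excludes increases in angle. It does not. The word *here* confines the sentence to the responder proportion, and signed values enter the angle, near-control and primary ANCOVAs. This stands, and it limits the point to per-child counts.

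**Other safety outcomes exist.** A reader might infer that deterioration is the only one. Acuity loss and diplopia are also tabulated, and diplopia is the first patching risk named in 1.9.1. Suppression grades are tabulated by arm (SAP 3.3), so a denser distribution in one arm would show. This stands too, but none of these counts worse control or a larger angle.

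**The cited series does not show harm.** A reader might take 19% and 39% as harm rates for patching. The protocol describes no control group for that series, 9 of the 31 children had prior surgery (an exclusion here), and rises were counted from 2 PD although the SAP's distance limits are 4 or 8 PD. Its 19% is close to the 17% implied by the plan's favourable scenario. The objection is right, and it is the reason for counting in both arms.

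**The rarity of deterioration is not established.** A reader might infer that the outcome will be empty, because among children not "treated during the study, only 1 (<1%) met motor or stereoacuity deterioration criteria at 3" years. That is a selected group: untreated children who completed the 3-year visit. Protocol 1.2.1 also reports 25 of 183 deteriorating by 3 years, 12 through treatment alone, leaving 13 on motor or stereoacuity criteria. Neither is a 3-month rate, and neither concerns patched children. The point rests on what the criteria require, not on how rare they are.

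**Conclusion.** The concern holds as a narrow gap in reporting. The protocol names worsening as a risk and points to criteria that can miss it; the proportion analyses of control and angle run one way, and no planned table counts the children who worsen. The documents do not show that patching causes worsening, and the primary analysis is unaffected.

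On the plan's own inputs, about 17% of patched and 40% to 42% of observed children would have some worsening of the distance control score. These figures assume normality for a bounded score that moves in steps. They take SDs informed by single control measures, while this trial averages three, and they include measurement noise. They show that some worsening is expected in both arms and cannot be read without the comparator; they are not forecasts of clinically important harm. The change is a cheap improvement and worth making.

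**What to change.** In SAP 8, add one descriptive table by arm, with number, percentage and 95% CI, no p-values, and outside the false discovery rate family:

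- (a) distance and near PACT increase beyond the test-retest cut-offs already in SAP 3.2;
- (b) mean distance and near control worse by 2 or more points, mirroring the improvement threshold in SAP 3.1.

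For (b), note that the scale stops at 5, so a child entering with a mean above 3.0 cannot worsen by 2 points; state how many children could.

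Include early outcome visits in this table, as the primary and secondary analyses do. SAP 8 now admits only visits within days 46 to 137, so a child brought in early for significant symptoms (Protocol 3.5) could drop out of the safety tables.

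Replace the sentence "only decreases in angle are of interest here" with a pointer to the new table. Counts of new esodeviation of 4 PD or more, and of suppression worse than baseline, are optional additions.

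The cost is SAP wording and one table from data already collected at both visits. There is no new procedure, no alpha cost and no change to the primary analysis. The drawback is small counts and low power, so the table should be labelled descriptive.

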3.3 Level of Suppression

- The proportion with each level of suppression (negligible, mild, moderate, or dense, as indicated on the
- completed follow-up worksheet) by treatment group at 3 months will be tabulated. The median and
- interquartile range for each group will be calculated and the distributions of suppression levels compared

between treatment groups at 3 months using the exact non-parametric Wilcoxon rank-sum test and twosample Hodges-Lehmann estimator.

4 Exploratory Analyses

Exploratory analyses will describe the distribution of the outcome, or change in outcome from baseline, within each treatment group and estimate treatment group differences and 95% confidence intervals (CIs), unless specified otherwise, with the purpose of identifying hypotheses for further study. All exploratory analyses will use observed data only without imputation for missing data. Only visits occurring within the analysis window will be included. As these are exploratory analyses, no adjustment for multiplicity will be made to confidence intervals and no p-values will be reported.

Continuous outcomes will be described using mean, standard deviation, and 95% CIs. Median and interquartile range (IQR) will also be reported if the outcome distribution is asymmetric. Treatment group differences and 95% CIs will be estimated using an ANCOVA model with adjustment for baseline level of the outcome. ANCOVA is relatively robust to violations of normality and homoscedasticity⁴; however, if ANCOVA model estimation of treatment group differences is of questionable validity due to violation of normality or other assumptions, actions to mitigate the violation will be undertaken. For example, for homoscedasticity violations, an ANCOVA model allowing the treatment groups to have different variances may be used and/or large outliers may be winsorized to the 5th and 95th percentiles of the overall outcome distribution (with treatment groups combined). In cases where winsorization of outliers is used, descriptive statistics for the treatment groups will be based on the outcome distribution after winsorization, and winsorized values will be noted in table/figure footnotes. Results of mitigated and original analyses will be compared for consistency, and results of both analyses reported if there are substantial differences.

Categorical outcomes will be described by tabulating the number and percentage falling into each category by treatment group at baseline and 3 months. For binary / dichotomized outcomes, the treatment group difference in percentages with the outcome at 3 months and 95% confidence interval will be estimated by inverting Barnard's test, using the method of Agresti and Min.² For multichotomous outcomes, no treatment group differences, or CIs, will be estimated as the sample sizes in each treatment group are small and sample size per outcome category is likely to be sparse.

